## Data Sources for Endpoints

AEs are from AE case report forms (CRFs).

Laboratory test results are from an external central laboratory and local laboratory test CRFs.

Migraine days per month, PoM categories, and SM categories are derived from subject-reported electronic diary (eDiary) data.

S-STS scores, MSQ scores, MIDAS scores, and CGI-c categories are derived from their respective CRFs.

### 3.2.1 Primary Objective Estimand

The estimand attributes corresponding to the primary endpoint for this study are shown in Table 1.

**Table 1: Primary Objective Estimands**

Objective	Safety and tolerability
Safety Endpoint	Number and percentage of subjects with AEs occurring in $\geq 5\%$ of treated subjects by intensity, SAEs, AEs leading to study drug discontinuation, and clinically significant laboratory abnormalities on treatment.  The frequency of AEs is based on the number and percentage of subjects with events. The frequency of clinically significant laboratory test abnormalities is determined from grade 3 to 4 laboratory tests, and based on the number and percentage of subjects with abnormalities among those with laboratory test data.
Summary	Frequency for the safety analysis set
Intercurrent Events	Study drug discontinuation: while-on-treatment strategy

### 3.2.2 Secondary Objective Estimands

Not applicable.

### 3.2.3 Exploratory Objective Estimands

The estimands corresponding to the exploratory objectives are shown in Table 2.

**Table 2: Exploratory Objective Estimands**

Objective	Frequency of AEs potentially associated with drug abuse
Safety Endpoint	Number and percentage of subjects with AEs potentially associated with drug abuse
Summary	Frequency for the safety analysis set
Intercurrent Events	Study drug discontinuation: while-on-treatment strategy
Objective	Frequency of AEs indicating medication-overuse headache
Safety Endpoint	Number and percentage of subjects with AEs indicating medication-overuse headache
Summary	Frequency for the safety analysis set
Intercurrent Events	Study drug discontinuation: while-on-treatment strategy
Objective	Frequency and intensity of hepatic-related AEs
Safety Endpoint	Number and percentage of subjects with hepatic-related AEs by intensity
Summary	Frequency for the safety analysis set
Intercurrent Events	Study drug discontinuation: while-on-treatment strategy
Objective	Frequency of LFT elevations based on fold changes above ULN
Safety Endpoint	Number and percentage of subjects with LFT elevations (ALT, AST, ALP or TBL) based on fold changes above ULN on treatment
Summary	Frequency for the safety analysis set with LFT data
Intercurrent Events	Study drug discontinuation: while-on-treatment strategy
Objective	Frequency of ALT or AST > 3x ULN concurrent with total bilirubin > 2x ULN
Safety Endpoint	Number and percentage of subjects with ALT or AST > 3x ULN concurrent with total bilirubin > 2x ULN on treatment
Summary	Frequency for the safety analysis set with LFT data
Intercurrent Events	Study drug discontinuation: while-on-treatment strategy
Objective	Frequency of ALT or AST > 3x ULN in temporal association with AEs
Safety Endpoint	Number and percentage of subjects with ALT or AST > 3x ULN concurrent with nausea, vomiting, anorexia, abdominal pain or fatigue on treatment
Summary	Frequency for the safety analysis set with LFT data
Intercurrent Events	Study drug discontinuation: while-on-treatment strategy

Objective	S-STS scores and changes from baseline
	For the ideation subscale, behavior subscale, and total scores: 
 
• Worst (highest) score on-treatment and follow-up
 
• Change from baseline to worst score on-treatment and follow-up
 
• Number and percentage of subjects in each of 5 worst change from baseline score categories (< -1, -1, no change, 1, > 1) on-treatment and follow-up
 

Safety Endpoint	
Summary	Summary statistics and frequency for the safety analysis set with S-STS data
Intercurrent Events	Study drug discontinuation: while-on-treatment strategy
Objective	Frequency of nasal edema and inflammation from nasal inspection
Safety Endpoint	Number and percentage of subjects with local irritation AEs
Summary	Frequency for the safety analysis set
Intercurrent Events	Study drug discontinuation: while-on-treatment strategy
Objective	Reduction from the OP in the number of migraine days per month by intensity
Safety Endpoint	Values and changes from OP in the number of migraine days per month during LTT (1) over time by month and (2) overall, by migraine intensity (total; moderate or severe)
Summary	Summary statistics for values and changes from OP over time for the migraine analysis set
Intercurrent Events	Study drug discontinuation: treatment policy strategy
Objective	MSQ domain scores and changes from baseline
Outcomes Research Endpoint	Values and changes from baseline in the MSQ score over time for each dimension
Summary	Summary statistics for values and changes from baseline over time for each dimension for the safety analysis set
Intercurrent Events	Study drug discontinuation: treatment policy strategy
Objective	PoM
Outcomes Research Endpoint	Number and percentage of subjects in each of 5 preference categories (much better to much worse) of study medication relative to previous migraine medications
Summary	Frequency for the safety analysis set with PoM data
Intercurrent Events	Study drug discontinuation: treatment policy strategy
Objective	SM
Outcomes Research Endpoint	Number and percentage of subjects in each of 7 satisfaction categories (completely satisfied to completely dissatisfied) of study medication
Summary	Frequency for the safety analysis set with SM data
Intercurrent Events	Study drug discontinuation: treatment policy strategy
Objective	MIDAS scores and changes from baseline
Outcomes Research Endpoint	Values and changes from baseline in the MIDAS score over time for each dimension
Summary	Summary statistics for values and changes from baseline over time for each dimension for the safety analysis set
Intercurrent Events	Study drug discontinuation: treatment policy strategy
Objective	CGI-c
Outcomes Research Endpoint	Number and percentage of subjects in each of 7 improvement categories (very much improved to very much worse) relative to investigator's past experience with other patients with the same diagnosis over time
Summary	Frequency over time for the safety analysis set with CGI-c data
Intercurrent Events	Study drug discontinuation: treatment policy strategy

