7.4 Study and Treatment Compliance

Responsible study personnel will dispense the study drug to the study subjects. Subjects should use all devices in one box/container before starting to use the devices in the next container. Accountability and compliance verification should be documented in the subject's study records.

Subjects must be counseled at all study visits on the importance of taking the study drug as directed. Treatment compliance, through review of study drug doses reported electronically, and review of the returned study drug, should be assessed by site staff at each study visit. Discrepancies between doses reported electronically, review of study drug, and information provided by subject, must be documented in the source record. Incorrect or missing dosing data and migraine data that are reported in the eDiary will be corrected through either a Data Clarification Record or a Medication Reconciliation Form, as appropriate.

Investigators should inform subjects that involuntary termination from the study will occur in cases where non-compliance is identified (defined as both non-compliance with the daily evening report and/or with average number of monthly doses of study drug). Study staff should contact a subject in between the monthly study visits if the subject demonstrates non-compliance the daily evening migraine report and document the contact in the source notes, to identify potential lost to follow up or non-compliant subjects as early as possible.

Investigators must monitor subjects for possible cases of abuse of study drug (patients taking study drug for non-therapeutic purposes, e.g. for psychoactive effects such as high or euphoria). Investigators should assess study drug accountability discrepancies (e.g. missing study drug, loss of drug, or non-compliance cases in which more study drug was used, as compared to expected). Investigators should obtain more information and explanation from patients when there are study drug accountability discrepancies. See Section 8.1.1.

Cases of potential study drug abuse or overdose (including cases of non-compliance with study drug dosing instructions or patients who discontinue treatment without returning study drug) should be documented in the source record and reported as an AE or SAE as appropriate. Dosing

errors (e.g. accidentally administering 2 sprays from 2 devices in one calendar day) should be reported as deviations.

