8.1 SERIOUS ADVERSE EVENT

8.1.1 Definition of Serious Adverse Event (SAE)

An SAE is any event that meets any of the following criteria at any dose:

- Death
- Life-threatening
- Inpatient hospitalization or prolongation of existing hospitalization
- Persistent or significant disability/incapacity
- Congenital anomaly/birth defect in the offspring of a subject who received study drug
- Other: Important medical events that may not result in death, be life-threatening, or require hospitalization, may be considered an SAE when, based upon appropriate medical judgment, they may jeopardize the subject and may require medical or surgical intervention to prevent one of the outcomes listed in this definition. Examples of such events are (but not limited to):
 - o Intensive treatment in an emergency room or at home for allergic bronchospasm

- o Blood dyscrasias or convulsions that do not result in inpatient hospitalization
- o Development of drug dependency or drug abuse
- o Potential drug induced liver injury (see Section 8.1.6)
- Abuse or Overdose of medication
 - Potential study drug abuse (including cases of excessive non-compliance with study drug dosing instructions or subjects who discontinue treatment without returning study drug) should be documented in the source record and reported as an AE or SAE as appropriate. Investigators must monitor subjects for possible cases of abuse of study drug (subjects taking study drug for non-therapeutic purposes, e.g. for psychoactive effects such as high or euphoria). Investigators should obtain more information and explanation from subjects when there are study drug accountability discrepancies
 - Potential study drug overdose is defined in Section 8.1.4.

Definition of Terms (the below applies to both non-serious adverse events and serious adverse events).

Mild: Is usually transient and may require only minimal treatment or therapeutic intervention. The event does not generally interfere with usual activities of daily living.

Moderate: Is usually alleviated with additional specific therapeutic intervention. The event interferes with usual activities of daily living, causing discomfort but poses no significant or permanent risk of harm to the subject.

Severe: Interrupts usual activities of daily living, significantly affects clinical status, or may require intensive therapeutic intervention.

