## Intercurrent Events

Intercurrent events are those that occur after treatment initiation and either preclude observation of the endpoint or affect its interpretation. Study drug discontinuation before the time point of interest defining the endpoint is considered an intercurrent event.

- For safety objectives, study drug discontinuation is handled with a “while-on-treatment strategy,” i.e., response to treatment prior to the occurrence of the intercurrent event of interest, such that all observed values of the endpoint of interest are used prior to study drug discontinuation.
- For outcomes research and other objectives, study drug discontinuation is handled with a “treatment policy strategy”, i.e., the occurrence of the intercurrent event is considered irrelevant, such that all observed values of the endpoint of interest are used regardless of study drug discontinuation.

Refer to Section 4.1 for analysis sets that are used to assess endpoints.

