#### 6.4.1.6 AEs in All Safety Analysis Periods Combined

AEs in all safety analysis periods combined (i.e., pre-treatment, on-treatment, and follow-up) are tabulated by SOC and PT for the safety analysis set for the following endpoints:

- AEs leading to study drug discontinuation
- Hepatic-related AEs leading to study drug discontinuation
- Local irritation AEs leading to study drug discontinuation.

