## 7.2 Analysis Periods

Analysis periods are defined as follows:

- OP: measurement date/time on or after the OP start date/time through the OP end date/time. This period is used to assess the number of migraine days per month during the OP.
- Pre-treatment: measurement date/time on or before the study drug start date/time. This period is used to derive baseline values, and to assess safety and outcomes research endpoints. Note that all measurements are pre-treatment for subjects in the enrolled analysis set with missing study drug start date.
- Pre-LTT: measurement date/time on or before the LTT start date/time. This period is used to derive analysis visit windows for slotting observations. Note that all measurements are pre-LTT for subjects in the enrolled analysis set with missing LTT start date.
- LTT: measurement date/time after the LTT start date/time through the LTT last date. This period is used to derive analysis visit windows for slotting observations, and to assess exposure and migraine days during LTT. Note that AEs with imputed start date equal to the

LTT start date are part of this period (refer to the Zavegeptan Core SAP for AE start date imputation).

- Follow-up: measurement date after the LTT last date. This period is used to slot observations.
- On-treatment safety: measurement date/time after the study drug start date/time through the study drug last date + 7 days. This period is used to assess safety endpoints on treatment.  
Note that AEs with imputed start date equal to the study drug start date are part of this period.
- Follow-up safety: measurement date after the study drug last date + 7 days. This period is used to assess safety endpoints during follow-up.

See Section 7.1 for derived dates for determining analysis periods. If measurement time is missing, not collected, or not applicable for a parameter, then the measurement date is compared to the derived date.

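### The exploratory drug-abuse endpoint closes 7 days after the last recorded spray, so abuse AEs for unreturned drug can fall outside it, and no table counts abuse AEs over the whole period after first dose

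*SAP*

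**What the plan says.** **What counts as potential abuse.** Protocol 8.1.1 describes it this way: "Potential study drug abuse (including cases of excessive non-compliance with study drug dosing instructions or subjects who discontinue treatment without returning study drug". Protocol 7.4 likewise names "patients who discontinue treatment without returning study drug" among cases of potential abuse or overdose. Both sections ask for documentation in the source record and for reporting as an AE or SAE as appropriate.

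**How the endpoint is defined.** The abuse row of SAP Table 2 reads "Number and percentage of subjects with AEs potentially associated with drug abuse", with the entry "Study drug discontinuation: while-on-treatment strategy". The intercurrent-event text in SAP 3.2 explains that strategy: "all observed values of the endpoint of interest are used prior to study drug discontinuation".

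**How it is delivered.** SAP 6.4.1.4 marks the table of potential drug abuse AEs as the exploratory endpoint and places it among on-treatment AEs. SAP 7.2 defines the on-treatment safety period as "measurement date/time after the study drug start date/time through the study drug last date + 7 days". Under SAP 7.1 the last date is that of the latest recorded spray, not that of the end-of-treatment visit or of the decision to stop.

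**What is combined across periods.** SAP 6.4.1.6 says "AEs in all safety analysis periods combined (i.e., pre-treatment, on-treatment, and follow-up) are tabulated by SOC and PT", but only for AEs leading to study drug discontinuation and, among those, the hepatic-related and local irritation ones.

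**The concern.** Most forms of abuse that the protocol describes, such as non-therapeutic use or excess dosing, happen while the subject is taking drug. Failure to return drug is different, because it arises when treatment stops and may be established only later. Dosing is as needed, visits after Week 4 are 4 weeks apart (Protocol 4.3), and final return is checked at the end-of-treatment visit (Protocol 4.3.5). A subject who stops attending is declared lost to follow-up only after repeated missed visits and contact attempts (Protocol 6.6.1). The date given to a non-return AE can therefore lie well after the last spray.

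Exploratory objective 1 asks for the frequency of AEs potentially associated with drug abuse. If non-return AEs belong to that group, a low figure in the designated table could partly reflect where the window closes. Missing drug is also a signal that Protocol 7.4 tells investigators to pursue.

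**Working it through.** The plan gives no figure on this point. Its only design figure, the one-sided 95% upper bound of 0.005 for no events in 600 subjects, reproduces as 1 − 0.05^(1/600) = 0.00498, but is not an input here.

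**Step 1: does the window fit the event?** An AE counts in the endpoint table if its date is no later than the last recorded spray + 7 days. A non-return AE dated at the stop of dosing, or within a week of it, is in. One dated later is out. So the table can miss such AEs, but does not have to.

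**Step 2: what share could be missed?** The documents do not say how a non-return AE is dated, and AE start-date imputation is deferred to the Core SAP. The range therefore has to be shown under assumptions. Let k be the number of doses per 28 days. Protocol 7.2.2 caps k at 8, and the infrequent-use rule in Protocol 6.6 suggests about 2 as a low value.

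- A. AE dated at the stop of dosing: share outside = 0.
- B. AE dated at an end-of-treatment visit falling at a random point in the dosing pattern. With random (Poisson) dosing, P(gap > 7 days) = exp(−7k/28) = exp(−k/4). With evenly spaced dosing it is max(0, 1 − k/4).
- C. As B with Poisson dosing, plus a detection delay uniform on 0 to 28 days: 21/28 + (1 − exp(−k/4))/k.

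| k per 28 days | A | B, Poisson | B, even spacing | C |
|---|---|---|---|---|
| 2 | 0% | 61% | 50% | 95% |
| 4 | 0% | 37% | 0% | 91% |
| 8 | 0% | 14% | 0% | 86% |

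For example, at k = 2, C gives 0.75 + (1 − 0.607)/2 = 0.947. Under B with Poisson dosing the share exceeds one half only when k < 4 ln 2 = 2.77. The spread of 0% to about 95% comes mainly from the dating rule.

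**Step 3: do other displays supply the missing count?**

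- The AE overview (SAP 6.4.1.2) has an abuse row and is run for follow-up AEs, but on the follow-up analysis set and separately from the on-treatment run. A subject with an abuse AE in both periods is counted in both, so the two counts cannot simply be added.
- The TEAE overview also has an abuse row. The TEAE definition is in the Core SAP, and SAP 6.4.1.4 handles TEAEs among on-treatment AEs.
- The listing of AEs of special interest (SAP 6.4.1) covers the enrolled set but gives no frequency.
- The accountability compliance table (SAP 6.2.6.2) counts subjects who did not return kits and discontinued. It treats anyone with a non-missing study drug last date as discontinued. SAP 7.1 derives that date for every treated subject whose study-completion question is answered, so completers are included. It also counts kits, not abuse AEs.

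None of these is specified to give the number of subjects with any abuse AE after first dose.

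**The case against.** The strongest reply is that little is lost. The 7-day extension keeps events at or just after the last spray. Non-return is only one example of potential abuse, and misuse during treatment is captured. Reporting is required only as appropriate, so not every unreturned kit becomes an AE. Abuse AEs receive the same on-treatment display as the other AEs of special interest, and SAP 6.4.1.6 does not single them out, since its hepatic and local irritation rows cover only AEs that lead to discontinuation. Later abuse AEs reach the follow-up overview and the listing, and missing drug is tabulated in SAP 6.2.6.2, with eDiary-versus-accountability differences in SAP 6.2.6.1. The follow-up set is a subset of the safety set, and AE dates feed the last contact date, so a subject with a follow-up AE would ordinarily be in it.

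All of that stands as fact, and it keeps the point small. It does not supply the single count that objective 1 calls for, for the reasons in step 3 of the working.

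Two further limits also stand. The definition of an abuse AE is in the Core SAP; if it excludes non-return, a wider window adds no such cases. And AE collection itself ends: non-serious AEs at the Follow-up Safety Visit (Protocol 8.3.1), SAEs 14 days after the last dose unless believed related to drug or study procedures (Protocol 8.1.3). Cases established after that may not be recorded as AEs at all, and a combined table would not recover them.

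**Conclusion.** The mismatch is real and minor. The protocol names an abuse event that arises at discontinuation, while the endpoint meant to count abuse AEs closes 7 days after the last recorded spray. Non-return AEs dated later can be missed from the designated frequency, and no other table combines the periods. The conclusion rests on two conditions that the available documents do not settle: that the Core SAP abuse definition includes non-return AEs, and that at least some are dated beyond the window.

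Three stronger readings are not supported.

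- A reader might infer that the endpoint misses most non-return cases. The share is 0% to about 95%, depending on a dating rule that is not given.
- A reader might take the strategy definition in SAP 3.2 literally and conclude that such events are excluded by construction. The operational period in SAP 7.2 admits those dated within 7 days of the last spray.
- A reader might attach a head count. Assuming that 3% to 8% of 600 subjects (18 to 48) leave without returning drug and that 75% to 100% of these fall outside the window gives about 14 to 48 subjects. The documents provide neither a non-return rate nor those percentages, and reporting as an AE is not automatic.

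**What to change.** Define the abuse row of SAP Table 2 over the on-treatment and follow-up safety periods combined, for the safety analysis set, and align its intercurrent-event entry so that AEs after discontinuation count. Add a line to SAP 6.4.1.6 for potential drug abuse AEs on or after study drug start; the restriction is needed because that section otherwise includes pre-treatment events. Keep the on-treatment table in 6.4.1.4. In the same edit, state whether non-return AEs belong to the abuse definition and how they are dated.

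The cost is SAP wording and one extra table from AE data already collected. The reported abuse frequency may be slightly higher.

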## 4 ANALYSIS SETS, TREATMENT GROUPS, AND SUBGROUPS

### 4.1 Analysis Sets

The following analysis sets are evaluated and used for presentation and analysis of the data:

- Enrolled: Subjects who sign an informed consent form and are assigned a subject identification number, i.e., non-missing informed consent date. This analysis set is used mainly to assess study population and in by-subject listings.
- LTT participated: Subjects in the enrolled analysis set who participated in the LTT phase, i.e., non-missing IWRS baseline visit date. This analysis set is used mainly to assess study population.
- Safety: Subjects in the enrolled analysis set who take study drug, i.e., non-missing study drug start date/time. This analysis set is used to assess study population, exposure, and on-treatment safety, migraine days per month, and outcomes research.
  - Migraine: Subjects in the safety analysis set with  $\geq 14$  days of data (not necessarily consecutive) in both the OP analysis period and  $\geq 1$  month in the LTT analysis period. This analysis set is used to assess migraine days per month.
  - Follow-up: Subjects in the safety analysis set whose last contact date is in the follow-up safety analysis period. This analysis set is used to assess follow-up safety.
- Full: Subjects in the LTT participated or safety analysis set.
- Coronavirus Disease 2019 (COVID-19) impacted: Subjects in the enrolled analysis set who are impacted by COVID-19 (see Section 9.1.2).

See Section 7.1 for derived dates and Section 7.2 for analysis periods.

